10.11 Pharmacokinetics

Pharmacokinetic (PK) sampling will be more intensive for the letrozole arm. Letrozole is considered to be a sensitive substrate for CYP3A4. BYL719 is likely to decrease letrozole clearance via its potent irreversible inhibition of CYP3A4, with a potential considerable increase in both letrozole systemic drug exposure and its elimination half-life. The increase in the elimination half-life is expected to delay the attainment of steady-state, which may only be reached after several weeks. Although letrozole is not known to have serious toxicities

(potential toxicities include hot flashes, arthralgias, fatigue, and bone density loss over time), pharmacokinetic sampling has been designed to carefully evaluate the potential drug-drug interaction with BYL719.

In contrast, the risk for drug-drug interaction in the exemestane arm is considerably lower. In a clinical pharmacokinetic study, the specific inhibition of CYP 3A4 by ketoconazole showed no significant effects on the pharmacokinetics of exemestane. This data suggest that the fractional clearance of exemestane via CYP3A4 is not significant and therefore the impact of BYL719, a potent CYP3A4 inhibitor, on the oral drug clearance of exemestane can be considered low. Also, in vitro evidence showed that exemestane is metabolized not only through CYP3A4 but that alternative metabolic pathways such as aldoketoreductases exist. Exemestane does not inhibit any of the major CYP isoenzymes, indicating a low risk to affect BYL719 clearance. In addition, the available preclinical metabolism data of BYL79 indicate that CYP450 enzymes are unlikely to play a major role in BYL719 metabolism.

PK blood samples will be collected from all patients in the study. The sampling regimen assumes that both BYL719 and letrozole will be swallowed concomitantly, or less than 5 minutes apart; and both drugs will be taken at the same time every day.

The exact clock time of dosing as well as actual sample collection date and time and any sampling problems must be noted on appropriate source documentation. When patients come for the pre-dose PK (except for Cycle 1, Day 1) it should be noted when BYL719 and letrozole were taken the day before.

At the specified time points, 2.0 mL of blood will be collected in tubes containing EDTA. Plasma sample will be collected for BYL719 concentration measurement. Refer to the Laboratory Manual for detailed instructions for the collection, handling, and shipping of PK samples. Plasma concentrations of BYL719 will be measured by a laboratory designated by Novartis using a validated high-performance liquid chromatography (HPLC) method with tandem mass spectrometry (LC/MS/MS). Samples will be shipped for analysis to Novartis, Basel.

1. Please see laboratory manual for details regarding collection, shipping, and processing of PK samples.
2. Samples are to be stored at a minimum -70° Celsius until ready for shipment/analysis.

Pharmacokinetic (PK) sampling will be performed according to the table below for all study Arms. Also, if a patient experiences an adverse event that is related to BYL719, it is recommended to collect a blood sample for BYL719 PK.

Table 10-4 Pharmacokinetic sampling

	Arms A and C (Letrozole + BYL719)	Arm A Sample Number	Arms B and D (Exemestane + BYL719)	Arm B Sample Number
Cycle 1 Day 1	Predose	US101A	Predose	US130B

	30 min ± 6 min post dose 1 hr ± 15 min post dose 2 hr ± 15 min post dose 3 hr ± 15 min post dose 4 hr ± 15 min post dose 8 hr ± 1 hr post dose	US102A US103A US104A US105A US106A US107A	1 hr ± 15 min post dose 6 hr ± 30 min post dose	US131B US132B
Cycle 1 Day 15	Predose	US108A	Predose	US133B
Cycle 2 Day 1	Predose 30 min ± 6 min post dose 1 hr ± 15 min post dose 2 hr ± 15 min post dose 3 hr ± 15 min post dose 4 hr ± 15 min post dose 8 hr ± 1 hr post dose	US109A US110A US111A US112A US113A US114A US115A	Predose 1 hr ± 15 min post dose	US134B US135B
Cycle 2 Day 15	Predose	US116A	Predose 1 hr ± 15 min post dose	US136B US137B
Cycle 3 Day 1	Predose	US117A	Predose 1 hr ± 15 min post dose	US138B US139B
Cycle 4 Day 1	Predose	US118A	Predose	US140B
Cycle 5 Day 1	Predose	US119A	No PK	
Cycle 6 Day 1	Predose	US120A	No PK	
Cycle 8 Day 1	Predose	US121A	No PK	
Cycle 10 Day 1	Predose	US122A	No PK	
	Unscheduled	US1000A+	Unscheduled	US1000B+

10.12 Biopsy Specimen Processing and Analysis and Cell-free DNA (cfDNA) Studies

Pre-treatment, Day 15 on-treatment, and optional at-progression biopsies will be obtained to further define the biology of AI-resistance in metastatic ER+ breast cancer, and to evaluate predictive and pharmacodynamic biomarkers of treatment with BYL719. Pre-treatment and Day 15 on-treatment biopsies will be required, unless felt to put the patient at unacceptable risk (note: patients with bone-only metastases will have a pre-treatment biopsy only).

Patients will also be asked for their permission to store tissue for future use. All patients may be asked to undergo an optional tumor biopsy at progression, with the exact timing to be at the discretion of the investigator and patient (not necessarily within 28 days of last dose of BYL719), although a 2 week window is allowed

For retrospective feasibility and observational studies, tissue use at MSKCC is governed by the Human Biospecimen Utilization Committee (HBUC). The HBUC has trans-departmental and multidisciplinary representation. The HBUC reviews tissue-related applications for Exemptions for Existing Data (formerly Waiver of Authorization). The applicant will be asked to include information on the availability of the specific material that is being requested in the bank and its heritage, including information on the curation, the consent linked to the specimen (if any), and rarity of the resource including frequency of available and quantity of material.

Certain archived specimens have been obtained for specific purposes – for example, to determine protocol eligibility based on expression of a biologic determinant, or for pharmacodynamic assessments in association with a clinical trial. In the frozen specimen archive these purposes have been appropriately flagged in the specimen annotations, so that review committees and bank curators do not mistakenly authorize the use of such specimens for other than the purposes for which they were acquired.

Specimens will not be released if there is a concern with respect to amount of tumor available (i.e. a small tumor embedded in a single block); or if the request would deplete the MSKCC archive, unless MSKCC is specifically requested to do so by the patient. The HBUC will give special consideration to tissues requested for correlative analysis as part of a clinical trial, or to develop a tissue bank at an academic institution, cooperative group or corporate entity. In cases where specimens reside in local repositories curated by PI's of specific procurement protocols, the PI's are under the same obligation to seek HBUC (and other necessary) approval for use of the resource in their own studies as other investigators in the Center. This is so, because specimen resources are ultimately institutional resources, wherever they are stored and by whatever means they are ascertained. Approval of such studies by the HBUC will be by the same criteria as noted above. Special care should attend review of requests where approval would exhaust the resource.

In cases where specimens are needed fresh and will be used prospectively, the individual investigator needs to write an IRB biospecimen protocol. This protocol is fast-tracked through departmental and Research Council review and is reviewed at IRB by the expedited review process. This protocol is only for research that will be done on biospecimens obtained under specifically identified banking protocols and their informed consent and research authorization. The consent and research authorization for the use of the biospecimens will be waived as per 45 CFR 46.116(d) and 45 CFR 164.512(i)(2)(ii).

In collaboration with [name] (Department of Pathology), as we plan to perform massively parallel sequencing¹² of all exons corresponding to 230 cancer genes, including all currently druggable or "actionable" somatic mutations as well as additional oncogenes and tumor suppressor genes shown to have strong associations with cancer genesis and progression. The technique used to sequence exons of genes of interest¹³ and the technical implementation of an oncogene screening profile¹⁴ have been described previously. A small amount of tumor tissue is required for this sequencing platform (25ug of gross tissue, minimum 500ng DNA). Exonic DNA will be captured via solution-based hybrid selection¹² and sequenced on the Illumina HiSeq platform. The sequencing data will be analyzed for base mutations, insertions, deletions, copy number alterations and genomic rearrangements in all target genes, with germ-line DNA (whole blood) serving as a reference. Corroborating studies in cell lines will be performed in the lab of [name] (HOPP) in order to evaluate the biological plausibility of potential hits.

This approach has recently been used with success to identify genomic alterations underlying both drug sensitivity and resistance. In breast cancer, we have piloted this approach on a panel of 22 prospectively collected HER2 amplified metastatic tumors (MSKCC IRB # 06-163, [name] - PI) and have identified several mutations which may confer resistance to HER2-targeted therapy. Also using this platform, a TSC2 mutation was identified in a patient at MSKCC with advanced bladder cancer who had an uniquely favorable response to treatment with rapamycin on a clinical trial (personal communication, [name]). In a patient with *BRAF*-mutated melanoma who developed acquired resistance

to vemurafenib, a *MEK1* mutation was identified in the post-treatment sample that proved to confer resistance to RAF inhibition with further corroborating studies.¹⁴ These results highlight the ability of a targeted, next generation sequencing approach to identify mechanisms of drug sensitivity and resistance.

In order to determine if pharmacodynamic markers of PI3K pathway hyperactivation and inhibition (e.g. P-AKT, P-S6, P-4EBP) predict for PFS, we will also perform proteomic analysis of pre-treatment and on-treatment biopsies. When possible, Day 15 on-treatment biopsies should be performed from the same tumor site as the pre-treatment biopsies. The levels of pathway protein expression and their activation will be determined by Collaborative Enzyme Enhanced Reactive-immunoassay (CEER, Promethius Biosciences). CEER can be performed in a multiplexed fashion directly on clinical samples that may be available in limited amounts. This phosphoproteomic assay utilizes the formation of unique immuno-complexes between capture antibodies (Abs) printed on a nitrocellulose microarray surface, the target molecule (in cell lysate reacted with the slide), and two independent detector-Abs. One of the detector-Abs is conjugated to glucose oxidase (GO), and the other is conjugated to Horse Radish Peroxidase (HRP). Target detection requires the presence of both detector-Abs and the enzyme channeling event between GO and HRP will not occur unless both Abs are in close proximity. Using this assay, receptor tyrosine kinases and downstream pathway proteins can be detected at the single cell level (sensitivity of about 100 zeptomoles). Inpatient percent change in quantitative PI3K pathway activation signature will be scored and compared to percent tumor volume change at 8 week CT scan. The Spearman's rank correlation of inpatient percent change in PI3K pathway activation signature (measured as a continuous variable) with percent tumor volume change at 8 week CT scan (measured as a continuous variable) will be calculated to evaluate whether pharmacodynamic markers of PI3K pathway inhibition are predictive of response to therapy. We will also perform immunohistochemistry on a paraffin block to evaluate for PTEN loss. This may be performed on archival primary tumor block or archival metastatic tumor if not enough tumor is available from the pre-treatment metastatic biopsy. PTEN will be scored as 0 (PTEN loss), 1 or 2, as previously described for breast cancer tissue by [name] at MSKCC¹⁴. Specifically, the cytoplasmic and/or nuclear immunoreaction will be scored based on intensity whereby a score of 2 = positive (equal in intensity to normal epithelial cells), a score of 1 = weak (reduced intensity as compared with normal epithelial cells), and a score of 0 = negative (no immunoreaction).¹⁵

Sequencing data will be analyzed for base mutations, insertions, deletions, and copy number alterations. Corroborating studies in cell lines will be performed in the lab in order to evaluate the biological plausibility of potential hits. Results of correlative studies will be primarily descriptive and provide the preliminary evidence necessary to recommend specific biomarkers for future clinical study or new drug development.

Tumor specimen macrodissection will be performed in the MSK clinical pathology department. Immunohistochemistry for PTEN will be performed in the lab of [name] (Department of Surgery, Breast Service). DNA isolation and targeted sequencing analysis will be performed in the lab of [name] (Department of Pathology). Proteomic analyses and corroborating studies in cell lines will be performed in the lab of [name] (Department of Medicine, HOPP).

The detection of tumor derived fragments of DNA in a blood sample provides the opportunity for relatively non-invasive serial assessment of the genetic alterations harbored in the tumor. Optimally the analysis of cfDNA will be used to determine tumor mutation status for patients in whom a biopsy is not feasible and serial assessment for new genetic alterations that occur during tumor progression and therapeutic resistance ([Forsheo, Murtaza et al. 2012](#); [Misale, Yaeger et al. 2012](#); [Murtaza, Dawson et al. 2013](#)). Small studies have begun to examine the clinical utility of cfDNA; quantitatively as a prognostic biomarker and specifically as a surrogate for tumor burden and response to treatment by quantifying known somatic mutations identified in the tumor ([Spindler, Pallisgaard et al. 2012](#); [Dawson, Tsui et al. 2013](#)). Incorporation of formal testing for its predictive utility in prospective studies examining pathway inhibition with targeted therapy is currently under investigation.

cfDNA will be extracted and quantified by qPCR under the direction of [name] [name] (Department of Medicine, [name] Lab) at intervals designated in Table 10-1. Known *PIK3CA* mutations will be serially quantified by dPCR in the Genomic Core Facility. Additional mutations identified by targeted exome sequencing will undergo dPCR assay design and validation.

12.1 CRITERIA FOR THERAPEUTIC RESPONSE/OUTCOME ASSESSMENT

The primary objective of this study is to determine the recommended phase II dose of BYL719 when administered in combination with either letrozole or exemestane. As of January 2014, this trial is being amended such that an additional primary objective is to determine the recommended phase II dose of BYL719 administered in a 7 day on, 7 day off schedule, in combination with letrozole, and the recommended phase II dose of BYL719 administered on a 5 day on, 2 day off schedule, in combination with exemestane. All patients who receive at least one dose of BYL719 will be evaluable for toxicity assessment. See Section 9.3 for the definitions of dose limiting toxicities and Section 9.4 for the dose-finding schema.

In order to estimate the efficacy of BYL719 plus letrozole or exemestane (a secondary endpoint), we will calculate the following for each arm separately in the expansion cohort only:

- a. Progression-free survival (PFS) will be examined using Kaplan-Meier methods.
- b. Overall response rate (ORR = complete response (CR) plus partial response (PR)) will be calculated with an exact confidence interval.
- c. Clinical benefit rate at 16 weeks (CBR = CR + PR + stable disease) will be calculated with an exact confidence interval.
- d. Time to treatment failure (TTF) will be examined using Kaplan-Meier methods.

The RECIST criteria version 1.1 will be used to evaluate therapeutic response. All patients who receive at least one week of BYL719 in combination with letrozole or exemestane will be evaluable for response. Patients with measurable or non-measurable lesions are included in this study. Measurable lesions are defined as those that can be measured accurately in at least one diameter, that is ≥ 20 mm using conventional imaging techniques (including incremental CT) or ≥ 10 mm using spiral CT equipment. Non-measurable lesions include bony metastases, leptomeningeal disease, ascites, pleural/pericardial effusions, inflammatory breast cancer, lymphangitic carcinomatosis, and heavily calcified and cystic/necrotic lesions.

Patients will have an evidence of disease (EOD) evaluation at baseline, consisting of CT of chest/abdomen +/- pelvis (with oral and IV contrast unless contraindicated) and a bone scan. Patients will then have EOD evaluation with CT of chest/abdomen +/- pelvis every two cycles (8 weeks) for the first four cycles (16 weeks) of study treatment (Day 1 +/- 7 days of Cycle 3 and Cycle 5), and then every 3rd cycle (12 weeks) thereafter (Day 1 +/- 7 days of Cycle 8, Cycle 11, etc). EOD evaluation will occur every 4th cycle (16 weeks) +/- 4 weeks from the last evaluation for patients who are on study under Amendment 13. A bone scan will also be performed if the baseline bone scan showed evidence of osseous metastatic disease (otherwise, a bone scan is not required, but may be obtained at the investigator's discretion if clinically indicated). For patients with locally-advanced unresectable breast cancer, radiographic assessments using MRI scans are acceptable to evaluate response, and a CT scan of chest/abdomen is not required.

For equivocal findings of progression (e.g., very small and uncertain new lesions, cystic changes or necrosis in existing lesions, or other such equivocal findings), treatment may continue until the next scheduled assessment at the discretion of the treating physician. If, at the next scheduled assessment, progression is confirmed, the date of progression should be the earlier date when progression was suspected.

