14.2 Dose-Finding Phase

The purpose of the dose-finding portion of the study is to determine the recommended phase II dose of BYL719 in combination with a fixed dose of either letrozole or exemestane. For Arm A and Arm B, the five proposed doses of BYL719 are 200mg, 250mg, 300mg, 350mg or 400mg. For Arms C and D, the five proposed doses of BYL719 are 150mg, 200mg, 250mg, 300mg, and 350mg.

The plans for dose escalation or de-escalation consist of entering patients in cohorts of three. The specific details are given in Section 9.4. Dose-limiting toxicities are defined in Section 9.3. All patients within a cohort will be observed for toxicity for one cycle (28 days) prior to entering patients at the next dose level. If a patient discontinues study participation during the first cycle (within 28 days of starting study treatment) for reasons unrelated to an adverse event or disease progression, an additional patient may be enrolled to replace that subject. We expect this early dropout to be a rare event, occurring 5% of the time, and will be examined closely as a source for potential bias. Otherwise, all patients who receive at least one dose of BYL719 in combination with letrozole or exemestane will be evaluable for toxicity. All patients who receive at least one week of BYL719 in combination with letrozole or exemestane will be evaluable for response.

The probability that dose escalation or de-escalation will occur at any stage during this portion of the study is a function of the underlying DLT rate at the current dose level. This probability can be calculated as the sum of the binomial probabilities of the following two outcomes that would permit escalation to occur:

1. No DLT observed in the first three patients.
2. One DLT is observed in the first three patients followed by no DLT observed in three additional patients at the same dose level.

The true risk of toxicity is expected to be in the range of 10%-40%. The following table shows the corresponding probabilities of dose escalation:

True Risk of Toxicity	.10	.20	.30	.40
Probability of Escalation	.91	.71	.49	.31

These numbers show that the probability of escalating to the next dose level is large when the underlying true toxicity rate is small and the probability of escalating decreases appropriately as the true toxicity rate increases.

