14.3 Expansion Phase

In the expansion portion of the study, 10 additional patients will be enrolled in each arm, Arm C and Arm D, in order to further define the safety and feasibility of BYL719 in combination with letrozole or exemestane at the established dose from the dose-finding phase, and to estimate the efficacy of this combination.

In order to help ensure that the DLT rate observed among the additional 10 patients in each arm is consistent with the DLT rate observed at the established dose from the dose-finding portion, the following decision rule will be implemented for each of the two study arms. If ≥ 4 DLTs are seen at any time in any one expansion arm, then it is likely that the safe and tolerable dose determined during the first portion of the trial is too toxic. The safety data will then be reviewed with the primary investigator and Novartis to determine how to move forward. Depending on the circumstances, we may consider de-escalating the dose of BYL719 to the next lower dose level and accruing 10 additional patients at that level. The probability of observing at least 4 patients with a DLT in the 10 additional patients is .28 if 1 of 6 patients were seen with a DLT in the dose-finding phase of the study. The probability of observing at least 4 patients with a DLT in the 10 additional patients is .09 if 0 of 6 patients were seen with a DLT in the dose-finding phase of the study.¹¹ The below table provides additional details on the probability of observing at least 1 to 9 patients with DLTs in the expansion cohort of 10 patients given that 0 or 1 patient in the initial dose-finding cohort of 6 patients had a DLT.¹¹

DLTs in dose-finding cohort	DLTs in expansion cohort								
	1 DLT (of 10)	2 DLTs	3 DLTs	4 DLTs	5 DLTs	6 DLTs	7 DLTs	8 DLTs	9 DLTs
0 (of 6)	0.59	0.33	0.18	0.09	0.04	0.02	0.01	<0.01	<0.01
1(of 6)	0.85	0.64	0.44	0.28	0.16	0.08	0.04	0.01	0.01

The two arms of the study will be monitored in tandem, and we have added an overall sequential global stopping rule to be applied as both expansion cohorts are accruing. We include this early stopping rule across both arms because the mechanism and toxicities of both AIs are known to be very similar. Our global stopping rule is based on repeated significance testing and serves as a global safety measure. We assume a grade 4 toxicity rate of 10% as acceptable and 35% as unacceptable. With these assumptions, if 2 of the

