14.4 Secondary Objectives

There are several planned secondary analyses. Selected non-hematologic and hematologic toxicities will be described, as measured by the NCI Common Toxicity Criteria, version 4.0, with the maximum grade over all cycles used as the summary measure per patient.

In order to estimate the efficacy of BYL719 plus letrozole or exemestane, we will calculate the following for each arm, Arm C and Arm D separately in the expansion cohort only:

- a. Progression-free survival (PFS) will be examined using Kaplan-Meier methods.
- b. Overall response rate (ORR = complete response (CR) plus partial response (PR)) will be calculated with an exact confidence interval.
- c. Clinical benefit rate (CBR = CR + PR + stable disease at 16 weeks) will be calculated with an exact confidence interval.
- d. Time to treatment failure (TTF) will be examined using Kaplan-Meier methods.

Pharmacokinetic parameters such as AUC and C_{max} of daily BYL719 will be calculated.

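### The one-week threshold for response evaluability would leave any week-1 stopper out of the secondary ORR and CBR denominators, which can only raise those rates or leave them unchanged

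*Combined protocol and SAP*

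**What the plan says.** Section 12.1 defines two populations. For safety: "All patients who receive at least one dose of BYL719 will be evaluable for toxicity assessment". For response: "All patients who receive at least one week of BYL719 in combination with letrozole or exemestane will be evaluable for response". Section 14.2 repeats the response rule.

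Section 14.3 sets the expansion size: "10 additional patients will be enrolled in each arm, Arm C and Arm D". Section 14.4 restricts the efficacy analysis: "we will calculate the following for each arm, Arm C and Arm D separately in the expansion cohort only". The two rates concerned are "Overall response rate (ORR = complete response (CR) plus partial response (PR)) will be calculated with an exact confidence interval" and "Clinical benefit rate (CBR = CR + PR + stable disease at 16 weeks", the latter also with an exact interval. Neither the confidence level nor the denominator is written out.

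Scans after baseline are scheduled "every two cycles (8 weeks) for the first four cycles (16 weeks) of study treatment", so the first planned on-study assessment is at week 8.

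No section gives an all-treated denominator for ORR or CBR, says how a patient without an on-treatment scan is counted, or plans a sensitivity analysis. Section 14.2 allows replacement of some early dropouts, but in the dose-finding phase, and this does not settle the expansion denominators.

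**The concern.** Whether a patient enters the response set depends on what happens after she starts treatment. Someone who stops in the first week, for toxicity, clinical deterioration or refusal, has been given the regimen and has not benefited. She cannot be stable on treatment at 16 weeks, and a response at an early end-of-treatment scan is very unlikely. Leaving her out removes a failure from the denominator and nothing from the numerator.

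In a cohort of 10, one patient is a tenth of the data. The same patient could count as a DLT under the section 14.3 decision rule and be absent from the efficacy rates reported beside it.

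The threshold is also loose. Arm D doses on days 1-5 and 8-12 (Table 9-1). One week could mean 7 calendar days, which contain 5 doses, or 7 dosing days, the seventh being day 9. On Arm C the two readings coincide. Section 10.10.2 allows a hold of up to 7 days in Cycle 1, and nothing says how a hold in the first week counts.

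**Working it through.** The plan states no target, power or precision for ORR or CBR, so there is no figure of its own to reproduce.

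**Inputs**
- Expansion size per arm: 10 (section 14.3).
- Response set: one week or more of treatment (sections 12.1 and 14.2).
- Cycle 1 dropout: 5% over 28 days, for reasons other than adverse events or progression (section 14.2, dose-finding).
- Assumed, because the documents do not give them: x responders (3) or patients with benefit (5); k patients stopping before one week (1 or 2); a 95% confidence level.

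**Step 1: direction.** The all-treated rate is x/10 and the evaluable-set rate is x/(10 − k). Their ratio is 10/(10 − k): 1.11 for k = 1 and 1.25 for k = 2. The difference is x·k/[10(10 − k)], which is zero only when x = 0 and positive otherwise.

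**Step 2: size, with Clopper-Pearson 95% intervals.**

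| Assumed count | All treated (n = 10) | One excluded (n = 9) | Two excluded (n = 8) |
|---|---|---|---|
| 3 responders | 30.0% (6.7 to 65.2) | 33.3% (7.5 to 70.1) | 37.5% (8.5 to 75.5) |
| 5 with benefit | 50.0% (18.7 to 81.3) | 55.6% (21.2 to 86.3) | 62.5% (24.5 to 91.5) |
| 0 responders | 0% (upper limit 30.8) | 0% (33.6) | 0% (36.9) |

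One exclusion adds 3·1/90 = 3.3 points at 3 responders and 5·1/90 = 5.6 points at 5 with benefit. Two exclusions add 3·2/80 = 7.5 and 5·2/80 = 12.5 points. For comparison, the interval for 3/10 is 65.2 − 6.7 = 58.5 points wide.

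**Step 3: how likely an exclusion is.** If each patient has first-week loss probability d, the chance that at least one of 10 is excluded is 1 − (1 − d)^10.

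| First-week loss d | At least 1 of 10 | At least 2 of 10 |
|---|---|---|
| 1% (assumed) | 9.6% | 0.4% |
| 1.27% (5% over 28 days, spread evenly) | 12% | 0.7% |
| 5% (assumed) | 40% | 8.6% |
| 10% (assumed) | 65% | 26% |

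The 1.27% is 1 − 0.95^(1/4). It is a rough guide only: the 5% omits adverse events and progression, and comes from the dose-finding phase ("We expect this early dropout to be a rare event, occurring 5% of the time").

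**The case against.** The strongest reply is that the rule may never bite. It does nothing unless an expansion patient receives less than one week of treatment, and the documents suggest this is uncommon. Rash, the main DLT on daily dosing, generally appeared at days 10-14 (section 3.7), after the threshold. Rapidly progressive or extensive symptomatic visceral disease is excluded at entry (6.3.15), the AI must already have been tolerated (6.2.6), and a short hold in Cycle 1 need not be a stop. The rule does not require a post-baseline scan, so failures between the first week and week 8 stay in. All of this stands. The limit is that the single-agent DLTs in section 3.5.2 were hyperglycemia, nausea and vomiting, with no onset times, so rash timing alone does not show that week-1 loss is negligible.

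It is also fair that exclusion is only implied by the word evaluable. But no other denominator is offered, so an analyst would have little else to follow.

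A reader might go further in four ways that the documents do not support:
- That the reported rates are inflated. Nothing shows that any expansion patient stopped in week 1.
- That ORR is biased upward overall. Patients with non-measurable disease are admitted and may pull ORR down, so the net direction is not established.
- That the arms face different thresholds of 7 and 5 doses. This is one reading. On a calendar reading the threshold is equal, and the arms are not randomised and are analysed separately.
- That having different safety and efficacy populations is itself a defect. Both were defined prospectively; the problem is only what the response set leaves out.

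**Conclusion.** The point holds in conditional form. As written, the plan would leave out of the ORR and CBR denominators any expansion patient who stops before one week, and such an exclusion can only raise the rates or leave them unchanged. At the assumed counts, one exclusion adds 3.3 to 5.6 percentage points, against an exact interval about 59 points wide for 3/10. The two-exclusion figures show the arithmetic but have no anchor in the documents.

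This rests on reading evaluable as defining the denominator, on treating a week-1 stopper as a non-responder, and on a 95% level. Week-1 loss is probably uncommon. ORR and CBR are secondary estimates with no target or decision rule, so the recommended phase II dose and the safety rules are unaffected. It remains worth correcting because the direction is known and the repair needs no new data.

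**What to change.** In sections 12.1, 14.2 and 14.4:
- calculate ORR and CBR per arm among all expansion patients who received at least one dose of BYL719;
- count patients without an on-treatment assessment as non-responders;
- report the one-week evaluable set alongside as a sensitivity analysis, stating whether one week means calendar days or dosing days.

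Section 1.0 records that accrual closed after 51 patients, so this would be a post-accrual change. If results already exist, report both denominators rather than substitute one for the other.

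The cost is wording and one extra set of estimates, with no new patients, visits or data. The downside is that the stated rates may be slightly lower.
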